2. Visit 2/Baseline, Day 1 can also be Visit 6/Week 12, Day 85 of Study SGT-54-01 or Study SGT-54-02

3. Visit 3/Week 4, Day 29 (± 10 Days)
4. Visit 4/Week 8, Day 57 (± 10 Days)
5. Visit 5/Week 12, Day 85 (± 10 Days)
6. Visit 6/Week 16, Day 113 (± 10 Days)
7. Visit 7/Week 20, Day 141 (± 10 Days)
8. Visit 8/Week 24, Day 169 (± 10 Days)
9. Visit 9/Week 28, Day 197 (± 10 Days)
10. Visit 10/Week 32, Day 225 (± 10 Days)
11. Visit 11/Week 36, Day 253 (± 10 Days)
12. Visit 12/Week 40, Day 281 (± 10 Days)/ End of Treatment/End of Study for patients who complete the study, early terminate, or if the Sponsor terminates the study prematurely.

The study product will be administered in an open-label fashion, i.e., the treatment assignment will be known to the patient, to study personnel and Sol-Gel personnel and its representatives.

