8.1.3 Visit Windowing

For subjects receiving S5G4T-1 in 54-01/54-02, data from 54-01/54-02 will be included in summaries of 54-07. For subjects receiving vehicle in 54-01/54-02, baseline values will be sourced from 54-01/54-02 and data from follow-up visits of 54-07 will be used in summaries. The table below details the analysis visits to be summarized and the associated visits from 54-01/54-02 or 54-07 which will be sourced for each type of subject.

Analysis Visits for Efficacy and Safety Assessments

Analysis Visit	Subjects Receiving S5G4T-1 in 54-01/54-02	Subjects Receiving vehicle in 54-01/54-02
Week 4	54-01/02 - Week 4	54-07 - Week 4
Week 8	54-01/02 - Week 8	54-07 - Week 8
Week 12	54-01/02 - Week 12	54-07 - Week 12
Week 16	54-07 - Week 4	54-07 - Week 16
Week 20	54-07 - Week 8	54-07 - Week 20
Week 24	54-07 - Week 12	54-07 - Week 24
Week 28	54-07 - Week 16	54-07 - Week 28
Week 32	54-07 - Week 20	54-07 - Week 32
Week 36	54-07 - Week 24	54-07 - Week 36
Week 40	54-07 - Week 28	54-07 - Week 40
Week 44	54-07 - Week 32	Not available
Week 48	54-07 - Week 36	Not available
Week 52	54-07 - Week 40	Not available

Data from 54-07 will be mapped to the appropriate analysis visit described above based on nominal visit indications. Data from Early Termination (ET) and unscheduled visits will be determined using analysis visit windows. The analysis visit windows for ET and unscheduled visits are presented in the following table.

SGT-54-07 Analysis Visit Windows for Efficacy and Safety Assessments

Nominal Visit	Target Study Day¹	Window (Days)
Week 4	29	22 to 42
Week 8	57	43 to 70
Week 12	85	71 to 98
Week 16	113	99 to 126
Week 20	141	127 to 154
Week 24	169	155 to 182
Week 28	197	183 to 210
Week 32	225	211 to 238
Week 36	253	239 to 266
Week 40	281	267 to 294
Week 44	309	295 to 322
Week 48	337	323 to 350
Week 52	365	351 to 378

¹ Number of days since nominal Baseline visit of 54-07

Data collected at ET and unscheduled visits prior to study day 22 will not be analyzed. Data collected at ET and unscheduled visits after study day 378 will not be included in analyses.

The definition for the study day included in each study window is defined as below:

Study Day prior to Day 1 = Visit Date – Day 1 Date

Study Day on or after Day 1 = Visit Date – Day 1 Date + 1

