8.9.2 Adverse Events

AEs from 54-01/02 will be included in the analysis for 54-07. All AEs that were reported as ongoing in 54-01/02 will be added into the CRF for 54-07, while AEs reported as recovered/resolved will be pulled forward programmatically into 54-07.

AEs occurring during the study will be recorded and classified on the basis of MedDRA terminology. Descriptions of AEs will include the date of onset, the date the AE ended, the severity of the AE, the relationship to study product, the action taken regarding study product usage, the action taken to treat the AE, and the outcome. All reported treatment-emergent AEs (TEAEs) will be summarized by the number of patients reporting AEs, system organ class, severity, seriousness, and relationship to study product. TEAEs are those AEs with an onset on or after the date of the first study product application. For AEs recorded in the 54-07 study if the AE is not indicated as prior to first application on the CRF then it will be considered a TEAE. AEs from 54-01/02 for subjects who received S5G4T-1 in 54-01 or 54-02 will be considered a TEAE if they were considered at TEAE in the 54-01/02 study. AEs (including ongoing) from 54-01/02 study for subjects who received vehicle in 54-01 or 54-02 will be considered pre-treatment.

AEs will be summarized by period (and total) and by severity. Each patient will be counted only once within a SOC or a Preferred Term by using the AEs with the highest severity within each category.

AEs will be summarized by period (and total) and by relationship to study product. Each patient will be counted only once within a system organ class or a preferred term by using the AEs with the greatest relationship within each category.

If relationship to study drug is reported as definitely, probably, or possible, then this is defined as related. If relationship to study drug is reported as unlikely or not related, then this is defined as unrelated.

TEAEs will be summarized in total as well as by the following periods based on time of onset in relation to date of first application of S5G4T-1, based on the definitions below. Start dates will be imputed as described in Section 8.1.5.2.

- 0-12 Weeks $0 \leq \text{onset day} \leq 85$
- >12-28 Weeks $86 \leq \text{onset day} \leq 197$
- >28-52 Weeks $198 \leq \text{onset day} \leq 365$
- >52 Weeks $\text{onset day} \geq 366$

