10. CHANGES IN THE PLANNED ANALYSES

The protocol was written in a way that subjects who did not participate in 54-01 or 54-02 could be enrolled into 54-07. When the SAP was created, 54-07 was fully enrolled, and no subject was enrolled who did not complete the 54-01 or 54-02 study. The SAP was written such that any text from the protocol that discusses the new subjects was excluded.

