^a Counts reflect numbers of subjects reporting one or more adverse events that map to MedDRA. At each level of summarization (System Organ Class or Preferred Term) subjects are counted once under the greatest reported relationship.

Note: MedDRA Version 21.0.

Treatment-emergent adverse events are those events with an onset after the first application of E-BPO 5% Cream.

Related defined as “Definitely”, “Probably”, or “Possible”. Not Related defined as “Unlikely” or “Not related”.

SOURCE: USERNAME\SPONSOR\PROJECT\JOBNAME (DATE, TIME)

Table 14.3.1.3.1: Summary of Treatment-Emergent Adverse Event Characteristics - By Period
(Safety Population)
(Page 1 of 2)

	0-12 Weeks (N=xxx)	>12-28 Weeks (N=xxx)	>28-52 Weeks (N=xxx)	>52 Weeks (N=xxx)
Subjects Reporting Any Treatment-Emergent Adverse Event	xx (xx.x%)	xx (xx.x%)	xx (xx.x%)	xx (xx.x%)
Number of Treatment-Emergent Adverse Events	xx	xx	xx	xx
Subjects Reporting Any Serious Treatment-Emergent Adverse Event	xx (xx.x%)	xx (xx.x%)	xx (xx.x%)	xx (xx.x%)
Number of Serious Treatment-Emergent Adverse Events	xx	xx	xx	xx
Subjects Reporting Treatment-Emergent Adverse Event with Outcome of Fatal	xx (xx.x%)	xx (xx.x%)	xx (xx.x%)	xx (xx.x%)
Number of Treatment-Emergent Adverse Events with Outcome of Fatal	xx	xx	xx	xx
Subjects Who Discontinued Study Drug Due to a Treatment-Emergent Adverse Event	xx (xx.x%)	xx (xx.x%)	xx (xx.x%)	xx (xx.x%)
Number of Treatment-Emergent Adverse Events Leading to Discontinuation of Study Drug	xx	xx	xx	xx
Subjects Who Discontinued from the Study Due to a Treatment-Emergent Adverse Event	xx (xx.x%)	xx (xx.x%)	xx (xx.x%)	xx (xx.x%)
Number of Treatment-Emergent Adverse Events Leading to Discontinuation of Study	xx	xx	xx	xx

Note: Treatment-emergent adverse events are those events with an onset after the first application of E-BPO 5% Cream.

Related defined as “Definitely”, “Probably”, or “Possible”. Not Related defined as “Unlikely” or “Not related”.

Periods defined from date of first dose of E-BPO 5% Cream. Period >52 Weeks includes all adverse events reported after week 52 through the end of study participation.

By subject denominator for each period includes the number of subjects in the safety population completing the period or experiencing an adverse event during the period.

SOURCE: USERNAME/SPONSOR/PROJECT/JOBNAME (DATE, TIME)

Table 14.3.1.3.1: Summary of Treatment-Emergent Adverse Event Characteristics – By Period
(Safety Population)
(Page 2 of 2)

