XXXXXXXXXXXXXXXXXXXXXXXXXXXX	Severe	xx (xx.x%)	xx (xx.x%)	xx (xx.x%)	xx (xx.x%)
	Moderate	xx (xx.x%)	xx (xx.x%)	xx (xx.x%)	xx (xx.x%)
	Mild	xx (xx.x%)	xx (xx.x%)	xx (xx.x%)	xx (xx.x%)
XXXXXXXXXXXXXXXXXXXXXXXXXXXX	Severe	xx (xx.x%)	xx (xx.x%)	xx (xx.x%)	xx (xx.x%)
	Moderate	xx (xx.x%)	xx (xx.x%)	xx (xx.x%)	xx (xx.x%)
	Mild	xx (xx.x%)	xx (xx.x%)	xx (xx.x%)	xx (xx.x%)

^a Counts reflect numbers of subjects reporting one or more adverse events that map to MedDRA. At each level of summarization (System Organ Class or Preferred Term) subjects are counted once under the greatest reported severity. By subject denominator for each period includes the number of subjects in the safety population completing the period or experiencing an adverse event during the period.

Note: MedDRA Version 21.0

Treatment-emergent adverse events are those events with an onset after the first application of E-BPO 5% Cream.

Periods defined from date of first dose of E-BPO 5% Cream. Period >52 Weeks includes all adverse events reported after week 52 through the end of study participation.

SOURCE: USERNAME\SPONSOR\PROJECT\JOBNAME (DATE, TIME)

Table 14.3.1.5.4: Summary of Treatment-Emergent Serious Adverse Events by Relationship to Study Drug – By Period
 (Safety Population)
 (Page 1 of xx)

System Organ Class ^a Preferred Term	Relationship	0-12 Weeks	>12-28 Weeks	>28-52 Weeks	>52 Weeks
		(N=xxx)	(N=xxx)	(N=xxx)	(N=xxx)
XXXXXXXXXXXXXXXXXXXXXXXXXXXX	Related	xx (xx.x%)	xx (xx.x%)	xx (xx.x%)	xx (xx.x%)
	Not Related	xx (xx.x%)	xx (xx.x%)	xx (xx.x%)	xx (xx.x%)
XXXXXXXXXXXXXXXXXXXXXXXXXXXX	Related	xx (xx.x%)	xx (xx.x%)	xx (xx.x%)	xx (xx.x%)
	Not Related	xx (xx.x%)	xx (xx.x%)	xx (xx.x%)	xx (xx.x%)

^a Counts reflect numbers of subjects reporting one or more adverse events that map to MedDRA. At each level of summarization (System Organ Class or Preferred Term) subjects are counted once under the greatest reported relationship. By subject denominator for each period includes the number of subjects in the safety population completing the period or experiencing an adverse event during the period.

Note: MedDRA Version 21.0.

Treatment-emergent adverse events are those events with an onset after the first application of E-BPO 5% Cream.

Related defined as “Definitely”, “Probably”, or “Possible”. Not Related defined as “Unlikely” or “Not related”.

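### The by-period adverse event denominator depends on the outcome: adverse-event-free non-completers are dropped, non-completers with an event are kept, and completing the period is not defined

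*SAP*

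**What the plan says.** SAP 8.9.2 assigns treatment-emergent AEs (TEAEs) to four periods on the S5G4T-1 clock: "TEAEs will be summarized in total as well as by the following periods based on time of onset in relation to date of first application". The bounds are days 0-85, 86-197, 198-365, and 366 onward. That section gives no denominator. The rule appears only in the footnotes of the shells in SAP 12, Tables 14.3.1.3.1-4 and, for serious events, 14.3.1.5.1-4. There, the "denominator for each period includes the number of subjects in the safety population completing the period or experiencing an adverse event during the period". The footnotes time the periods from the first dose of the cream. For the last column they say: "Period >52 Weeks includes all adverse events reported after week 52 through the end of study participation".

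Three other places determine who can complete a period:

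- SAP 10 states that "no subject was enrolled who did not complete the 54-01 or 54-02 study", so every subject is a rollover.
- SAP 6.1 lists as the last visit "Visit 12/Week 40, Day 281 (± 10 Days)/ End of Treatment/End of Study for patients who complete the study".
- The visit map in SAP 8.1.3 has the row "Week 52 54-07 - Week 40 Not available". Its last entry is for former vehicle subjects, and their Weeks 44 and 48 are marked the same way.

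SAP 8.9.2 treats parent-study AEs of former vehicle subjects as pre-treatment, so their S5G4T-1 clock starts in SGT-54-07.

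**The concern.** A denominator should be fixed before the outcome is known. Here, of two subjects who leave during a period, the one with an AE is counted and the one without is not. The completers' data and the early leavers' events are combined, but the early leavers' event-free experience is discarded.

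AE frequency is part of the study objective, and Protocol 18.4 asks for tabulations by period. Readers will compare the columns to see whether AEs change with longer use. The >28-52 week column is the most exposed, because a whole subgroup is scheduled to finish partway through it. The pooled layout would not show this. Since completing is undefined, two programmers could also produce materially different tables from the same sentence.

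**Working it through.** The plan states no figure that depends on this rule, so there is none to reproduce.

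**1. Direction against period entry.** Let E be subjects entering a period, C those completing it, A_c completers with an AE and A_n non-completers with an AE.

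- Shell: (A_c + A_n)/(C + A_n).
- Period entry: (A_c + A_n)/E.

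The numerators are equal and C + A_n ≤ E, with strict inequality whenever an AE-free subject does not complete. This needs no assumption.

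**2. Day arithmetic.** Former vehicle subjects have their last visit at 281 ± 10, that is day 271 to 291 on the S5G4T-1 clock, or earlier on that clock if first use came after SGT-54-07 Baseline. The period is days 198-365, or 168 days. At day 281 they have been followed for 281 − 198 + 1 = 84 of them, which is half.

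**3. Assumptions.** The documents give no vehicle share, completion rate or AE risk. I take:

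- vehicle share v of period entrants 25%, 1/3 or 50%;
- completion c of 85%, 95% or 100% among former S5G4T-1 subjects, counting attendance at Week 52 as completing;
- full-period risk p of 10% or 20%, at constant hazard;
- early leavers observed for half their scheduled time, and leaving unrelated to AEs.

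Write h = 1 − (1 − p)^0.5 for half-period risk and q = 1 − (1 − p)^0.25 for quarter-period risk.

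**4. If completing means reaching Week 52.** Per entrant:

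- cases = (1 − v)[cp + (1 − c)h] + vh
- N = (1 − v)[c + (1 − c)h] + vh

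Example, v = 0.5, c = 0.85, p = 0.10, h = 0.0513: cases 0.0720, N 0.4545, printed 15.8%.

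| Vehicle share | p = 10% prints as (c = 100%, 95%, 85%) | p = 20% prints as (same c) |
|---|---|---|
| 25% | 11.5, 11.8, 12.5% | 22.7, 23.3, 24.5% |
| 1/3 | 12.3, 12.6, 13.4% | 24.0, 24.6, 26.0% |
| 50% | 14.4, 14.8, 15.8% | 27.6, 28.4, 30.0% |

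Printed over true risk runs from 1.14 (22.7/20) to 1.58 (15.8/10). These cells assume that all vehicle rollovers stay to their last visit. Giving them the same dropout lowers the top from 1.58 to 1.55.

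**5. If completing means finishing scheduled participation.** The vehicle terms become v[ch + (1 − c)q] in the cases and v[c + (1 − c)q] in N. With c = 85-95%:

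- Printed over period-entry percentage is 1.05 to 1.17.
- For vehicle shares of 1/3 to 1/2, printed over full-period risk is 0.78 to 0.91. A 25% share extends the top to 0.95 (v = 0.25, c = 0.85, p = 0.10: 0.0814/0.8567 = 9.5%).
- The period-entry percentage over full-period risk is 0.70 to 0.82 for the same shares. A 25% share extends the top to 0.86.

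**6. Unequal period lengths.** At constant hazard with full follow-up, risk over d days is 1 − (1 − p)^(d/168). For 85, 112 and 168 days this gives 5.2, 6.8 and 10.0% (p = 10%) or 10.7, 13.8 and 20.0% (p = 20%). With 85-95% completion the rule moves the 13.8% only to 14.1-14.9%.

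**7. The proposed rate.** At constant hazard, the rate per 100 patient-years is −ln(1 − p) × 365.25/168 × 100, which is 22.9 at p = 10% and 48.5 at p = 20%. A simulation with truncated follow-up and one person-time total per period returned 22.9 and 48.5.

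**The case against.** The strongest reply has four parts.

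- **The reading.** If completing means finishing scheduled participation, vehicle rollovers who attend Week 40 are counted and the structural problem disappears. This stands as a possible reading. Timing the periods from first dose favours the other, but the SAP does not settle it. A reader might infer that the >28-52 week column is necessarily the most inflated. That follows only on the Week 52 reading.
- **The direction.** A reader might also infer that the rule always overstates late AEs and so errs on the safe side. The documents do not support that. On the scheduled-participation reading, the printed figure is below full-period risk.
- **The remedy.** On that same reading, period-entry n/N lies further below full-period risk than the SAP rule does. This is correct, and it is why n/N should not be shown without a rate.
- **The weight.** The study is descriptive, the rule is printed on every shell, and part of any rise across columns comes from the period lengths. All true. None of it makes an outcome-dependent N interpretable.

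A reader might also conclude that the any-TEAE row of the >52-week column must print 100%, because an open-ended period cannot be completed. The footnote's reference to the end of study participation supplies a reasonable end. The point is only that the SAP should say so.

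**Conclusion.** The concern holds. As written, N depends on the outcome, and the percentage is never below the period-entry percentage. That part is certain. Its size, and its direction against full-period risk, depend on the meaning of completing and on quantities that the documents do not give:

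- On the Week 52 reading, the >28-52 week column prints at about 1.14 to 1.58 times full-period risk, for vehicle shares of 25-50%, completion of 85-100% among former S5G4T-1 subjects, and risks of 10-20% at constant hazard.
- On the scheduled-participation reading, the rule adds about 5-17% to the period-entry percentage with 5-15% dropout, and the result understates full-period risk because vehicle rollovers are seen for half the period.

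On neither reading can the percentages alone show a trend with longer use. The overall TEAE tables (14.3.1.2.1-4) and the by-period event counts are not affected. This should be corrected before the tables are run, but it does not undermine the study.

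**What to change.** 1. Delete the completers-or-cases sentence from the eight shells and state the denominator in SAP 8.9.2.
2. Use as N the Safety Population subjects still in the study on the first day of each period (days 1, 86, 198 and 366), and state that the last period ends with study participation. Footnote that n/N understates full-period risk where follow-up is truncated and that the periods differ in length. State how events reported after a subject's last visit are assigned, since Protocol 16.5 collects related serious events for 30 days after the last assessment.
3. Do not show this n/N alone. Beside it, in Tables 14.3.1.3.1 and 14.3.1.5.1, give events per 100 patient-years in study within the period. The shells already carry event counts, for example "Number of Treatment-Emergent Adverse Events Leading to Discontinuation of Study". Take person-time from the first-application and completion/discontinuation dates in Listing 16.2.1.1, because the SAP 8.9.1 exposure variables are not calculated for subjects lost to follow-up. Protocol 16.2 has severity changes entered separately, so state whether these count as separate events and keep rate numerators equal to the printed counts.
4. Show the by-period tables by parent-study arm as well as pooled, as SAP 8.1 provides.

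Cost: footnote edits on eight shells, one rule in SAP 8.9.2, a period-entry flag, and a person-time total per period and arm for two tables. No new data are needed. The downside is larger tables and modest extra programming.

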xxxxxx	xxxx	xxxxxxxxxx	xxxxxxxxxxxxxxxxxx	xxxxxxxxxx	xxxxxx xxxxx
xxxxxx	xxxx	xxxxxxxxxx	xxxxxxxxxxxxxxxxxx	xxxxxxxxxx	xxxxxx xxxxx
xxxxxx	xxxx	xxxxxxxxxx	xxxxxxxxxxxxxxxxxx	xxxxxxxxxx	xxxxxx xxxxx
xxxxxx	xxxx	xxxxxxxxxx	xxxxxxxxxxxxxxxxxx	xxxxxxxxxx	xxxxxx xxxxx

SOURCE: USERNAME\SPONSOR\PROJECT\JOBNAME (DATE, TIME)

Listing sorted by Subject.

Listing 16.2.1.1: End of Study Information
(Page xx of yy)

Subject	Age/Sex	Eval	Date of First Application	Date of Last Application	Date of Study Completion/Discontinuation (Day) ¹	Did Subject Complete the Study	Primary Reason for Study Discontinuation
xxxxxx	xxxx	xxxxxxxx	xxxxxxxxxx	xxxxxxxxxx	xxxxxxxxxxxxxxxx	xxx	
xxxxxx	xxxx	xxxxxxxx	xxxxxxxxxx	xxxxxxxxxx	xxxxxxxxxxxxxxxx	xx	xxxxxx xxxxx
xxxxxx	xxxx	xxxxxxxx	xxxxxxxxxx	xxxxxxxxxx	xxxxxxxxxxxxxxxx	xx	xxxx xx xxxxxxxxxxx xxxxxxxxxxx xxx xx xxxxxxxxxxx xxxxx xxxxx xxxxx xxx xxxx

¹ Day is calculated as date - date of first application of E-BPO 5% Cream (from SGT-54-01/SGT-54-02 or SGT-54-07) for dates prior to first application. Otherwise, day is calculated as date - date of first application + 1 for dates on or after first application.

SOURCE: USERNAME\SPONSOR\PROJECT\JOBNAME (DATE, TIME)

Listing sorted by Subject.

If Primary Reason for Study Discontinuation is Lost to Follow-Up, Protocol Violation, Withdrawal by Subject, or Other, the reason specification will be included following a colon (for example, WITHDRAWAL BY SUBJECT: xxxxx)

Listing 16.2.2.1: Inclusion/Exclusion Criteria
 (Page xx of yy)

Subject	Age/Sex	Eval	Criterion Failed	Description
xxxxxx	xxxx	xxxxxxxxxx	xxxxxx	xxxxx xxx xx xxxxxxxx xxxx xxxxxxxxxxxxxxxxxxxxxxxx xxxxxxxx
xxxxxx	xxxx	xxxxxxxxxx	xxxxxx	xxxxx xxx xx xxxxxxxx xxxx xxxxxxxxxxxxxxxxxxxxxxxx xxxxxxxx
xxxxxx	xxxx	xxxxxxxxxx	xxxxxx	xxxxx xxx xx xxxxxxxx xxxx xxxxxxxxxxxxxxxxxxxxxxxx xxxxxxxx
			xxxxxx	xxxxx xxx xx xxxxxxxx xxxx xxxxxxxxxxxxxxxxxxxxxxxx xxxxxxxx
			xxxxxx	xxxxx xxx xx xxxxxxxx xxxx xxxxxxxxxxxxxxxxxxxxxxxx xxxxxxxx xxxxxxxxxxxxxxxxxxxx xxxxxxxxx x xxxxxxxxxxxxxxxxxxxx xxx

SOURCE: USERNAME\SPONSOR\PROJECT\JOBNAME (DATE, TIME)

Listing sorted by Subject and Criterion Failed.

Listing 16.2.2.2: Screen Failure
 (Page xx of yy)

Subject	Age/Sex	Eval	Date of Screen Failure	Reason for Screen Failure
xxxxxx	xxxx	xxxxxxxxxx	xxxxxxxxxx	xxxxx xxx xx xxxxxxxx xxxx xxxxxxxxxxxxxxxxxxxxxxxx xxxxxxxx
xxxxxx	xxxx	xxxxxxxxxx	xxxxxxxxxx	xxxxx xxx xx xxxxxxxx xxxx xxxxxxxxxxxxxxxxxxxxxxxx xxxxxxxx
xxxxxx	xxxx	xxxxxxxxxx	xxxxxxxxxx	xxxxx xxx xx xxxxxxxx xxxx xxxxxxxxxxxxxxxxxxxxxxxx xxxxxxxx
			xxxxxxxxxx	xxxxx xxx xx xxxxxxxx xxxx xxxxxxxxxxxxxxxxxxxxxxxx xxxxxxxx
			xxxxxxxxxx	xxxxx xxx xx xxxxxxxx xxxx xxxxxxxxxxxxxxxxxxxxxxxx xxxxxxxx xxxxxxxxxxxxxxxxxxxx xxxxxxxxx x xxxxxxxxxxxxxxxxxxxxxx xxx

SOURCE: USERNAME\SPONSOR\PROJECT\JOBNAME (DATE, TIME)

Listing sorted by Subject.

Listing 16.2.2.3: Protocol Deviations
 (Page xx of yy)

Subject	Age/Sex	Eval	Deviation	Date (Day ¹)
xxxxxx	xxxx	xxxxxxxxxx	xxxxxx x xxxxxxxx xxx xx xxxxxxx xxxxxxx xxx xxx xx xxxxxxxxxxxxxxxx	xxxxxxxxxxxxxxxxxx
			xxxxxx xxx xx xxxxxxx xxxxxxx xxx xxx xx	xxxxxxxxxxxxxxxxxx
			xxxxxx x xxxxxxxx	
xxxxxx	xxxx	xxxxxxxxxx	xxxxxx xxx xx xxxxxxx xxxxxxx xxx xxx xx	xxxxxxxxxxxxxxxxxx
xxxxxx	xxxx	xxxxxxxxxx	xxxxxx xxx xx xxxxxxx xxxxxxx xxx xxx xx	xxxxxxxxxxxxxxxxxx

¹ Day is calculated as date - Baseline visit date from SGT-54-07 for dates prior to Baseline visit. Otherwise, day is calculated as date - Baseline date + 1 for dates on or after Baseline visit.

SOURCE: USERNAME\SPONSOR\PROJECT\JOBNAME (DATE, TIME)

Listing sorted by Subject and Date.

Listing 16.2.3: Analysis Populations
(Page xx of yy)

Subject	Age/Sex	Population	Included	Reason(s)	Excluded
xxxxxx	xxxx	Safety	xxx		
xxxxxx	xxxx	Safety	xxx		
xxxxxx	xxxx	Safety	xx	xxxxxxxxxxxx	xxxxxxx xxxxxxxxx

SOURCE: USERNAME\SPONSOR\PROJECT\JOBNAME (DATE, TIME)
Listing sorted by Subject and Population (as ordered above).

Listing 16.2.4.1: Subject Demographic Information
 (Page xx of yy)

Subject	Eval	B: Date of Birth A: Age S: Sex	R: Race E: Ethnicity	C: Childbearing Potential M: Method of Birth Control	Informed Consent Date
xxxxxx	xxxxxxxxxx	B: xxxx-xx-xx A: xx S: xxxxxx	R: xxxxxx xxxxxxxx xx xxxxx xxxxxxxx xxxxxxxx xxxxxxxx E: xxx xxxxxxxx xx xxxxxx	C: xxx M: xxxxxxxxxxx xxxxxxxx xxxxxxxxxxxxxxxx xxxxxxxx xxxx x xxxxxxxx xx xxxxxxxx xxxxxxxx xxxx xxxxxxxx	xxxx-xx-xx
xxxxxx	xxxxxxxxxx	B: xxxx-xx-xx A: xx S: xxxxx	R: xxxxxx E: xxxxxxxx xx xxxxxx	C: xx M:	xxxx-xx-xx
xxxxxx	xxxxxxxxxx	B: xxxx-xx-xx A: xx S: xxxxxx	R: xxxxxx E: xxxxxxxx xx xxxxxx	C: xxx M: xxxxxxxx xxxxxxxx	xxxx-xx-xx

SOURCE: USERNAME\SPONSOR\PROJECT\JOBNAME (DATE, TIME)

Listing sorted by Subject.

Listing 16.2.4.2.1: Unique Medical/Surgical History Coded to MedDRA System Organ Classes and Preferred Terms
 (Page xx of yy)

MedDRA System Organ Class	MedDRA Preferred Term	Medical/Surgical History Verbatim Term
xxxx xxx xxxxxxxxxxx xxxxxx xxxxxxxxxxx	xxxxxxx	xxxxxx
	xxxx xxxxxxxxxxx xxxxxxxx	xxxx xxxxxxxxxxx xxxxxx
xxxxxxxxxxx xxx xxxxxxxxxxxxxx	xxxxxxxxxxx	xxxxxxxxxxx
	xxxxxxxxxxxxxxxx	xxxxxxxxxxxxxxxx x xxxx xxx xxx
		xxxxxxxxxxxxxxxx xx xxxxx xx xxxx xxxxx xxx

Note: System Organ Class and Preferred Term map to MedDRA (Version 21.0).

SOURCE: USERNAME\SPONSOR\PROJECT\JOBNAME (DATE, TIME)

Listing sorted by System Organ Class, Preferred Term, and Verbatim Term.

Listing 16.2.4.2.2: Medical/Surgical History
 (Page xx of yy)

Subject	Age/Sex	Eval	Medical/Surgical History Verbatim Term	S: MedDRA System Organ Class P: MedDRA Preferred Term	S: Onset Date E: End Date
xxxxxx	xxxx	xxxxxxxx	xxxxxx	S: xxxx xxx xxxxxxxxxxxxxx xxxxxx xxxxxxxxxxxx P: xxxxxxxx	S: xxxx E:
			xxxxxxxx xx xxxxxxxxxxxxxx xxxxxxxxxxxx	S: xxxxxx xxxxxx xxxxxxxxxxxx P: xxxxxxxxxxx xxxxxx xxxxxxxx	S: xxxx E: xxxxxxxx
xxxxxx	xxxx	xxxxxxxx	xxxxxx	S: xxxx xxx xxxxxxxxxxxxxx xxxxxx xxxxxxxxxxxx P: xxxxxxxx	S: xxxx E:
xxxxxx	xxxx	xxxxxxxx	xxxxxx	S: xxxx xxx xxxxxxxxxxxxxx xxxxxx xxxxxxxxxxxx P: xxxxxxxx	S: xxxx E:
xxxxxx	xxxx	xxxxxxxx	xxxxxx	S: xxxx xxx xxxxxxxxxxxxxx xxxxxx xxxxxxxxxxxx P: xxxxxxxx	S: xxxx E:
			xxxxxxxxxxxxxxxxxxxxx	S: xxxxxx xxxxxx xxxxx P: xxxx xxxxxxxxxxxxxx	S: xxxxxxxxxxxx E: xxxxxxxx

Note: System Organ Class and Preferred Term map to MedDRA (Version 21.0).

SOURCE: USERNAME\SPONSOR\PROJECT\JOBNAME (DATE, TIME)

Listing sorted by Subject, Rosacea Diagnosis (all Rosacea MH will appear first), Onset Date, End Date, Verbatim Term

Listing 16.2.4.3.1: Unique Medication Names Coded to WHO Drug Global Dictionary ATC Level 2 Terms and Preferred Names
 (Page xx of yy)

WHO ATC Level 2 Term	WHO Preferred Name	Medication Verbatim Term	I: Indication T: Route
xxxxxxxxxxxxxx	xxxxxxxxxxxxxx	xxxxxxx	I: xxxxxxxxxx R: xxxxxxxxxx
		xxxxxxx	I: xxxxxxxxxx R: xxxxxxxxxx
xxxxxxxxxxxxxx	xxxxxxxxxxxxxx	xxxxxxx	I: xxxxxxxxxx R: xxxxxxxxxx
		xxxxxxx	I: xxxxxxxxxx R: xxxxxxxxxx

Note: ATC Level 2 Term and Preferred Name map to WHO Drug Global Dictionary, Format B3, Version March 1, 2018.

SOURCE: USERNAME\SPONSOR\PROJECT\JOBNAME (DATE, TIME)

Listing sorted by ATC Level 2 Term, Preferred Name, Medication Verbatim Term, Indication, and Route.

Listing 16.2.4.3.2: Prior and Concomitant Medications
(Page xx of yy)

S: Subject	A: ATC Level 2 Term	S: Start Date (Day) ¹	I: Indication	F: Frequency
A: Age/Sex	P: Preferred Name	E: End Date (Day) ¹	D: Dose	T: Route
E: Eval	M: Medication Name	P: Prior/Concomitant	U: Units	
S: xxxxxx	A: xxxxxxxxxxxx xxx xxxxxxxxxxxx	S: xxxxxxxxxxxxxxxxx	I: xxxxxxxx	F: xxx
A: xxxx	P: xxxxxxxxxxxx xxxxxxxx xxxxxxxxxxxxxxxx xxx xxxxxxxx xxx	E: xxxxxxxxxxxxxxxxx	D: xx	T: xxxxxxxxxxxxxxxx
E: xxxxxxxxxxxx	M: xxxxxxx xxxxx xxxxxxxxxxxx	P: xxxxxxxxxxxxxxxxx	U: xxxxxxxxxxxx	
	A: xxxxxxxx xx xxxxxxxx	S: xxxxxxxxxxxxxxxxx	I: xxxxxxxx	F: xx
	P: xxxxxxxxxxxx xxxxxxxx xxx	E: xxxxxxxxxxxxxxxxx	D: xx	T: xxxxx
	M: xxxxxxx xxxxxxxxxxxx	P: xxxxx	U: xxxxxxxx	
S: xxxxxx	A: xxxxxxxxxxxx xxx xxxxxxxxxxxx	S: xxxxxxxxxxxxxxxxx	I: xxxxxxxx	F: xxx
A: xxxx	P: xxxxxxxxxxxx xxxxxxxx xxxxxxxxxxxxxxxx xxx xxxxxxxx xxx	E: xxxxxxxxxxxxxxxxx	D: xx	T: xxxxxxxxxxxxxxxx
E: xxxxxxxxxxxx	M: xxxxxxx xxxxx xxxxxxxxxxxx	P: xxxxxxxxxxxxxxxxx	U: xxxxxxxxxxxx	
	A: xxxxxxxx xx xxxxxxxx	S: xxxxxxxxxxxxxxxxx	I: xxxxxxxx	F: xx
	P: xxxxxxxxxxxx xxxxxxxx xxx	E: xxxxxxxxxxxxxxxxx	D: xx	T: xxxxx
	M: xxxxxxx xxxxxxxxxxxx	P: xxxxx	U: xxxxxxxx	

¹ Day is calculated as date - date of first application of E-BPO 5% Cream (from SGT-54-01/SGT-54-02 or SGT-54-07) for dates prior to first application. Otherwise, day is calculated as date - date of first application + 1 for dates on or after first application.

Note: ATC Level 2 Term and Preferred Name map to WHO Drug Global Dictionary, Format B3, Version March 1, 2018.

SOURCE: USERNAME\SPONSOR\PROJECT\JOBNAME (DATE, TIME)

Listing sorted by Subject, Start Date, End Date, Medication Name, Indication, Route, Frequency. If the Route is Topical, then the area treated is presented within parenthesis (T: Topical (specify area)).

Listing 16.2.4.4.1: Unique Procedure/Therapy Names Coded to MedDRA System Organ Classes and Preferred Terms
(Page xx of yy)

MedDRA System Organ Class	MedDRA Preferred Term	Procedure/Therapy Verbatim Term	Indication
xxxxxxxxxxxxxxxx	xxxxxxxxxxxxxxxx	xxxxxxxx xx xxxxx	xxxxxxxxxxxx
		xxxxxxxx	xxxx xx xxxx
xxxxxxxxxxxxxxxx	xxxxxxxxxxxxxxxx	xxxxxxxx	xxxxxxxx
			xxxxxxxxxxxx
		xxxxxxxx	xxxxxxxxxxxx
xxxx xx xx xxxxxx	xxxxxx xxxxxxx xxx	xxxxxxxx xxxxxx	xxxxxxxx xxxxxxx xx xx xxxxx

Note: System Organ Class and Preferred Term map to MedDRA (Version 21.0).

SOURCE: USERNAME\SPONSOR\PROJECT\JOBNAME (DATE, TIME)

Listing sorted by System Organ Class, Preferred Term, Verbatim Term, and Indication.

Listing 16.2.4.4.2: Prior and Concomitant Procedures/Therapies
(Page xx of yy)

Subject	Age/Sex	Eval	S: MedDRA System Organ Class P: MedDRA Preferred Term M: Procedure/Therapy Name	S: Start Date (Day) ¹ E: End Date (Day) ¹ P: Prior/Concomitant	I: Indication A: Anatomical Area Treated
xxxxxx	xxxx	xxxxxxxx	S: xxxxxxxx xxx xxxxxxxx xxxxxxxx P: xxxxxxxxxxxx xxxxxxxxxxxx xxxxxxxx M: xxxxxxxx xxxxx xxxxxxxx xxxxxxxx	S: xxxxxxxxxxxxxxxxxxxx E: xxxxxxxxxxxxxxxxxxxx P: xxxxxxxxxxxxxxxxxxxx	I: xxxxx xxxxxxx A:
xxxxxx	xxxx	xxxxxxxx	S: xxxxxxxx xxx xxxxxxxx xxxxxxxx P: xxxxxxxxxxxx xxxxxxxxxxxx xxxxxxxx M: xxxxxxxx xxxxx xxxxxxxx xxxxxxxx	S: xxxxxxxxxxxxxxxxxxxx E: xxxxxxxxxxxxxxxxxxxx P: xxxxxxxxxxxxxxxxxxxx	I: xxxxx xxxxxxx A:
xxxxxx	xxxx	xxxxxxxx	S: xxxxxxxx xxx xxxxxxxx xxxxxxxx P: xxxxxxxxxxxx xxxxxxxxxxxx xxxxxxxx M: xxxxxxxx xxxxx xxxxxxxx xxxxxxxx	S: xxxxxxxxxxxxxxxxxxxx E: xxxxxxxxxxxxxxxxxxxx P: xxxxxxxxxxxxxxxxxxxx	I: xxxxx xxxxxxx A:
			S: xxxxxxxx xxxxxxxx xxxxx P: xxx xxxxxxxxxxxx xxxxxxxx M: xxxxxxxx xxxxxxxx	S: xxxxxxxxxxxxxxxxxxxx E: xxxxxxxxxxxxxxxxxxxx P: xxxxxxxxxxxxxxxxxxxx	I: xxxxxxxxxxx xxxxx xx xx A: xxxxxxxxxxx
			S: xxxxxxxx xxxxxxxx xxxxx P: xxx xxxxxxxxxxxx xxxxxxxx M: xxxxxxxx xxxxxxxx	S: xxxxxxxxxxxxxxxxxxxx E: xxxxxxxxxxxxxxxxxxxx P: xxxxxxxxxxxxxxxxxxxx	I: xxxxxxxxxxx xxxxx xx xx A: xxxxxxxxxxx

¹ Day is calculated as date - date of first application of E-BPO 5% Cream (from SGT-54-01/SGT-54-02 or SGT-54-07) for dates prior to first application. Otherwise, day is calculated as date - date of first application + 1 for dates on or after first application.

Note: System Organ Class and Preferred Term map to MedDRA (Version 21.0).

SOURCE: USERNAME\SPONSOR\PROJECT\JOBNAME (DATE, TIME)

Listing sorted by Subject, Start Date, End Date, Procedure/Therapy Name, and Indication.

Listing 16.2.5.1: Study Visit Compliance
(Page xx of yy)

Subject	Age/Sex	Eval	Visit	SGT-54-07 Analysis Visit	Visit Date	Day ¹	Within Study Window ²	Reason Screening And Baseline Visit Occurred on Different Days	Reason for Unscheduled Visit
xxxxxx	xxxx	xxxxxxxx	xxxxxxxx	xxxxxxxx	xxxxxxxx				
			xxxxxxxx	xxxx x	xxxxxxxx			xxxxxxx xxx xx	
			xxxx x	xxxx x	xxxxxxxx				
			xxxx x	xxxx x	xxxxxxxx				
			xxxx xx	xxxx x	xxxxxxxx				
			xxxx xx	xxxx x	xxxxxxxx				
			xxxx xx	xxxx x	xxxxxxxx	xx	xxx		
			xxxx xx	xxxx x	xxxxxxxx	xx	xxx		
			xxxx xx	xxxx x	xxxxxxxx	xx	xxx		
			xxxx xx	xxxx x	xxxxxxxx	xx	xxx		
			xxxx xx	xxxx x	xxxxxxxx	xx	xxx		
			xxxx xxxxx	xxxx x	xxxxxxxx	xx	xxx		
			xxxx xx	xxxx x	xxxxxxxx	xx	xxx		xxxxxxxxxxxxxxxx
			xxxx xx	xxxx x	xxxxxxxx	xx	xxx		
			xxxx xx	xxxx x	xxxxxxxx	xx	xxx		
			xxxx xx	xxxx x	xxxxxxxx	xx	xxx		
			xxxx xx	xxxx x	xxxxxxxx	xx	xxx		xxxxxxxxxxxxxxxx
			xxxx xx	xxxx x	xxxxxxxx	xx	xxx		
			xxxx xx	xxxx x	xxxxxxxx	xx	xxx		
			xxxx xx	xxxx x	xxxxxxxx	xx	xxx		
			xxxx xx	xxxx x	xxxxxxxx	xx	xxx		xxxxxxxxxxxxxxxx
			xxxx xx	xxxx x	xxxxxxxx	xx	xxx		
			xxxx xx	xxxx x	xxxxxxxx	xx	xxx		
			xxxx xx	xxxx x	xxxxxxxx	xx	xxx		

¹ Day is calculated as date - Baseline date from SGT-54-07 for dates prior to Baseline visit. Otherwise, day is calculated as date - Baseline date + 1 for dates on or after Baseline visit. Day is only calculated for visits occurring in SGT-54-07.
² Determined by protocol-specified visit window for scheduled visits after Baseline. Only assessed for visits occurring in SGT-54-07.

SOURCE: USERNAME\SPONSOR\PROJECT\JOBNAME (DATE, TIME)

Listing sorted by Subject and Visit Number.

Listing 16.2.5.2: Subject Dosing Compliance
(Page xx of yy)

Subject	Age/Sex	Eval	Date of First Application	Date of Last Application	Number of Days of Exposure	Total Number of Applications	Number of Instructed Missed Applications ¹	Number of Non-Instructed Missed Applications ²
xxxxxx	xxxx	xxxxxxxx	xxxxxxxxxx	xxxxxxxxxx	xx	xxx	xx	xx
xxxxxx	xxxx	xxxxxxxx	xxxxxxxxxx	xxxxxxxxxx	xx	xxx	xx	xx
xxxxxx	xxxx	xxxxxxxx	xxxxxxxxxx	xxxxxxxxxx	xx	xxx	xx	xx
xxxxxx	xxxx	xxxxxxxx	xxxxxxxxxx	xxxxxxxxxx	xx	xxx	xx	xx
xxxxxx	xxxx	xxxxxxxx	xxxxxxxxxx	xxxxxxxxxx	xx	xxx	xx	xx

¹ The number instructed missed applications is the total number of missed doses on the CRF with reason "Per PI Instruction".

² The number of non-instructed missed applications is the total number of missed doses on the CRF with reason of "Other, specify reason".

SOURCE: USERNAME\SPONSOR\PROJECT\JOBNAME (DATE, TIME)

Listing sorted by Subject.

Listing 16.2.5.3: Subject Dosing
(Page xx of yy)

Subject	Age/Sex	Eval	Study Interval	Start Date	End Date	Number of Doses Applied ¹ or Number Of Doses Applied Each Day of the Date Span ²	Reason Subject Did Not Dose or Dosed More Than Once Per Day ²
xxxxxx	xxxx	xxxxxxxx	54-01 First to Last Dose Interval	xxxxxxxx	xxxxxxxx		
			54-01 Dosing Deviation	xxxxxxxx	xxxxxxxx	x	
			54-01 Dosing Deviation	xxxxxxxx	xxxxxxxx	x	
			54-01 Dosing Deviation	xxxxxxxx	xxxxxxxx	x	
			54-07 Dosing Interval	xxxxxxxx	xxxxxxxx	x	xxx xx xxxxxxxx
			54-07 Dosing Interval	xxxxxxxx	xxxxxxxx	x	
			54-07 Dosing Interval	xxxxxxxx	xxxxxxxx	x	xxx xx xxxxxxxx
			54-07 Dosing Interval	xxxxxxxx	xxxxxxxx	x	
			54-07 Dosing Interval	xxxxxxxx	xxxxxxxx	x	xxx xx xxxxxxxx
xxxxxx	xxxx	xxxxxxxx	54-01 First to Last Dose Interval	xxxxxxxx	xxxxxxxx		
			54-01 Dosing Deviation	xxxxxxxx	xxxxxxxx	x	
			54-01 Dosing Deviation	xxxxxxxx	xxxxxxxx	x	
			54-01 Dosing Deviation	xxxxxxxx	xxxxxxxx	x	
			54-01 Dosing Deviation	xxxxxxxx	xxxxxxxx	x	
			54-07 Dosing Interval	xxxxxxxx	xxxxxxxx	x	xxx xx xxxxxxxx
			54-07 Dosing Interval	xxxxxxxx	xxxxxxxx	x	
			54-07 Dosing Interval	xxxxxxxx	xxxxxxxx	x	
xxxxxx	xxxx	xxxxxxxx	54-07 Dosing Interval	xxxxxxxx	xxxxxxxx	x	xxx xx xxxxxxxx
			54-07 Dosing Interval	xxxxxxxx	xxxxxxxx	x	
			54-07 Dosing Interval	xxxxxxxx	xxxxxxxx	x	xxx xx xxxxxxxx
			54-07 Dosing Interval	xxxxxxxx	xxxxxxxx	x	
			54-07 Dosing Interval	xxxxxxxx	xxxxxxxx	x	xxx xx xxxxxxxx
			54-07 Dosing Interval	xxxxxxxx	xxxxxxxx	x	
			54-07 Dosing Interval	xxxxxxxx	xxxxxxxx	x	xxx xx xxxxxxxx

¹ From SGT-54-01 or SGT-54-02

² From SGT-54-7

Note: Dosing from the SGT-54-01 or 54-02 study was pulled forward for only subject who received E-BPO 5% Cream in the Phase 3 study.

SOURCE: USERNAME\SPONSOR\PROJECT\JOBNAME (DATE, TIME)

Listing sorted by Subject and Start Date of Dosing Interval.

Listing 16.2.5.4: Study Medication Dispensation
(Page xx of yy)

Subject	Age/Sex	Eval	Visit	Date of Dispensation	Pump Number Assigned	Instructions Given to the Subject by the Investigator Regarding When to Apply the Study Product	Reason Why a New Pump Was Not Dispensed
xxxxxx	xxxx	xxxxxxxx	xxxxxxxx	xxxxxxxx	xxxx	xxxxxxxxxx xxxx xx x x xxxx xxxx	
			xxxx x	xxxxxxxx	xxxx	xx xxxx xxxxxxxx xx x x xxxxxx xx	
			xxxx x	xxxxxxxx	xxxx	xxxxxxxx xxxxxxxxxx xxxx xx x x xxxx xx	
			xxxx x	xxxxxxxx	xxxx	xxxx x xxx	
			xxxx x	xxxxxxxx	xxxx	xxxx xx xxxx xxxxxxxx xx x x xxxxxxxx	
			xxxx x	xxxxxxxx	xxxx	x xxxxx xxx xx	
			xxxx x	xxxxxxxx	xxxx	xxxxxxxxxx xxxx xx x x xxxx xxxxx	
xxxxxx	xxxx	xxxxxxxx	xxxxxxxx	xxxxxxxx	xxxx	xxxxxxxx xxxx xx x x xxxx xxxx	
			xxxx x	xxxxxxxx	xxxx	xx xxxx xxxxxxxx xx x x xxxxxx xxxxxx	
			xxxx x	xxxxxxxx	xxxx	xxxxxxxxxx xxxx xx x x xxxx xxxxxx	
			xxxx x	xxxxxxxx	xxxx	xxxx x xxx	
			xxxx x	xxxxxxxx	xxxx	xxxx xx xxxx xxxxxxxx xx x x xxxxxx	
			xxxx x	xxxxxxxx	xxxx	xxxxx x xxxxx xxx xx	
			xxxx x	xxxxxxxx	xxxx	xxxxxxxxxx xxxx xx x x xxxx xxxxx	
			xxxx x	xxxxxxxx	xxxx	xxxx xx xxxx xxxxxxxx xx x x xxxxxxxx	
			xxxx x	xxxxxxx	xxxx		x xxxxx xxxxx
							xxxxxxxxxx xx
							xxx x xxx xxx
			xxxx x	xxxxxxxx	xxxx	xxxx xx xxxx	
			xxxx x	xxxxxxxx	xxxx	xxxxxxxxxx xxxx xx x x xxxx xxxxxx	
			xxxx x	xxxxxxxx	xxxx	xxxx xx xxxx xxxxxxxx xx x x xxxxxx xxxxxx	
			xxxx x	xxxxxxxx	xxxx	x xxxxx xxx xx	
			xxxx x	xxxxxxxx	xxxx	xxxxxx xxxxx xx x x xxxxx xxxxx xxx xxx	
			xxxx x	xxxxxxxx	xxxx	xxxxxxxxxx xxxx xx x x xxxx xxxxxx	

SOURCE: USERNAME\SPONSOR\PROJECT\JOBNAME (DATE, TIME)

Note to programmers: If a pump was not dispensed, NOT DONE will print in the date column. Listing sorted by Subject and Visit Number.

Listing 16.2.5.5: Study Medication Accountability Log
 (Page xx of yy)

Subject	Age/Sex	Eval	Pump Number	Dispensing		Return		Amount Used (g)	
				Date	Weight (g)	Date	Weight (g)		
xxxxxx	xxxx	xxxxxxxx	xxxx	xxxxxxxxxx	xxxx	xxxxxxxxxx	xxxx	xxxx	
				xxxxxxxxxx	xxxx	xxxxxxxxxx	xxxx	xxxx	
				xxxxxxxxxx	xxxx	xxxxxxxxxx	xxxx	xxxx	
				xxxx	xxxxxxxxxx	xxx	xxxxxxxxxx	xxxx	xxxx
				xxxx	xxxxxxxxxx	xxxx	xxxxxxxxxx	xxxx	xxxx
				xxxx	xxxxxxxxxx	xxxx	xxx xxxx	xxxx	xxxx
				xxxx	xxxxxxxxxx	xxxx	xxxxxxxxxx	xxxx	xxxx
				xxxx	xxxxxxxxxx	xxxx	xxxxxxxxxx	xxxx	xxxx
xxxxxx	xxxx	xxxxxxxx	xxxx	xxxxxxxxxx	xxxx	xxxxxxxxxx	xxxx	xxxx	
				xxxx	xxx xxxx				
				xxxx	xxxxxxxxxx	xxxx	xxxxxxxxxx	xxxx	xxxx
				xxxx	xxxxxxxxxx	xxxx	xxxxxxxxxx	xxxx	xxxx
xxxxxx	xxxx	xxxxxxxx	xxxx	xxxxxxxxxx	xxxx	xxxxxxxxxx	xxxx	xxxx	
				xxxx	xxxxxxxxxx	xxxx	xxxxxxxxxx	xxxx	xxxx
				xxxx	xxxxxxxxxx	xxxx	xxxxxxxxxx	xxxx	xxxx
				xxxx	xxxxxxxxxx	xxxx	xxxxxxxxxx	xxxx	xxxx

SOURCE: USERNAME\SPONSOR\PROJECT\JOBNAME (DATE, TIME)

Listing 16.2.6.3.1: RosaQoL Descriptions
(Page xx of yy)

Number	RosaQoL Question
1	I worry that my rosacea may be serious
2	My rosacea burns or stings
3	I worry about getting scars from my rosacea
4	I worry that my rosacea may get worse
5	I worry about side effects from rosacea medications
6	My rosacea is irritated
7	I am embarrassed by my rosacea
8	I am frustrated by my rosacea
9	My rosacea makes my skin sensitive
10	I am annoyed by my rosacea
11	I am bothered by the appearance of my skin (redness, blotchiness)
12	My rosacea makes me feel self-conscious
13	I try to cover up my rosacea (with make-up)
14	I am bothered by persistence/reoccurrence of my rosacea
15	I avoid certain foods or drinks because of my rosacea
16	My skin feels bumpy (uneven, not smooth, irregular)

SOURCE: USERNAME\SPONSOR\PROJECT\JOBNAME (DATE, TIME)

Listing 16.2.6.3.1: RosaQoL Descriptions
(Page xx of yy)

Number	RosaQoL Question
17	My skin flushes
18	My skin gets irritated easily (cosmetics, aftershaves, cleansers)
19	My eyes bother me (feels dry or gritty)
20	I think about my rosacea
